3.3. Measurements

3.3.1. Exposure Definition

IBA+OBR

Defined as either 800mg IBA every 2 weeks + OBR (TMB-202), or 800mg IBA every 2 weeks + OBR following a 2000mg IBA loading dose (TMB-301/311) (see [Table 1](#))

vs.

Non-IBA OBR

Defined as the first HTE-indicative regimen initiated within the study period in the OPERA cohort, after resistance has been established. Recycling of ARVs from prior regimens is allowed. Viral sensitivity/susceptibility to at least one ARV in the regimen.

3.3.2. Outcome Definition

Virologic outcomes:

- Viral suppression (<200 copies/mL)
- Undetectable VL (<50 copies/mL)

Timepoints of interest:

Weeks 24, 48, 60, 96 after index (closest measurement within a ± 6 -week window)

3.3.3. Covariates

Covariates for the propensity score model

The following characteristics are available in the TMB-202, TMB-301/311 and OPERA datasets. These baseline covariates are candidates for inclusion in the PS model.

- Age
- Sex
- Viral load
- CD4 cell count

- Index date
- OBR
- Resistance to ARVs
- Number of potent ARV received as part of index regimen, scaled by the level of resistance a patient has to these ARVs
 - Provides a measure of the number of potent ARVs which formulates each patient's OBR, where the influence of each ARV is scaled by relative resistance to that drug class
 - Based on the number of ARVs a patient is currently receiving for which they display mutations corresponding to resistance level (RL) 1-5 [see [Error! Reference source not found.](#)]
 - For each regimen, weighting of the level of resistance will be calculated using [Equation 1](#)

Equation 1

$$Weight = \sum_1^n \frac{ARV_n \times (5 - RL)}{5} + \frac{DRV \times (4 - RL)}{4}$$

Where:

ARV_n = DTG, TDF, TAF, FTC, 3TC or ETR; 1 if present, 0 if absent

DRV = 1 if DRV present, 0 if DRV absent

RL = Resistance Level [see [Error! Reference source not found.](#)]

Table 2. Categories included in drug class-specific mutation variable

Specific Drug	B Presence of Mutations or Patterns that Confer Extremely High-Level Resistance	C Presence of Mutations or Patterns that Confer High-Level Resistance	D Presence of Mutations or Patterns that Confer Intermediate-Level Resistance	E Presence of Predictive Mutations but Activity Not Impacted	F
	Category 4 Required Mutations	Category 3 Required Mutations or Score	Category 2 Required Mutations or Score	Category 1 Required Mutations or Score	Notes
DTG	Q148H, Q148K, Q148R + any three of the following L74I, L74M T97A E138A, E138K, E138T G140A, G140C, G140S	Q148H, Q148K, Q148R + any two of the following L74I, L74M T97A E138A, E138K, E138T G140A, G140C, G140S	Q148H, Q148K, Q148R + any one of the following L74I, L74M T97A E138A, E138K, E138T G140A, G140C, G140S	Two or more of the following: T66A, T66I, T66K E92Q T97A Y143R, Y143C, Y143H V151I N155H	NA
DRV	NA	Darunavir Score ≥12 (consistent with high-level resistance)	Darunavir Score 7-11 (consistent with intermediate-level resistance)	Darunavir Score ≤6	Add the score for each of these mutations to create a total DRV score: 4 each: I50V, L76V, I84V, I54MV 3 each: V32I, L33F, I47AV, I54L, V82F 2 each: V11I, G73S, L89V
TDF, TAF	NA	Includes one of: K65R, K65N Without M184V, M184I	Includes one of: K65R, K65N With M184V or M184I	NA	M184V/I confers resistance to other drugs but increases sensitivity to TDF, TAF
FTC, 3TC	NA	Includes one of: M184V, M184I	Includes one of: K65R, K65N	NA	NA
ETR	NA	Includes one of: K101P, Y181I, Y181V OR Two of: L100I, K101EH, Y181C, G1190E, G190Q, H221Y	Includes one of: L100I, K101EH, Y181C, G190E, G190Q, H221Y	NA	NA

Covariates for the multiple imputation model

The following characteristics are available in OPERA but may or may not be available in the TMB-202 and TMB 301/311 datasets. These baseline and time-updated characteristics may be used for the multiple imputation model, as predictors of the value of viral loads at timepoints of interest.

- Age at regimen initiation
- Sex at regimen initiation
- Race
- HBV co-infection at regimen initiation
- HCV co-infection at regimen initiation
- AIDS (ever)
- Viral load at each timepoint
- Viral loads in between timepoints
- Timing of viral loads
- CD4 cell count at each timepoint
- CD4 cell count in between timepoints
- Timing of CD4 cell counts
- Index date
- ARVs in index regimen
- Resistance to ARVs
- Number of anchor agent classes exposure prior to index

4. Data Analyses

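### Table 2 names G1190E in the high-level ETR list where the adjoining list names G190E; coded as written, Equation 1 scores ETR 0.2 of a drug too high for the people affected

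*Combined protocol and SAP*

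**What the plan says.** Equation 1 in section 3.3.3 sums a term for each drug in the index regimen. For DTG, TDF, TAF, FTC, 3TC and ETR the term is (5 − RL)/5; for DRV it is (4 − RL)/4. RL is the resistance level, and Table 2 gives the mutation rules.

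In the ETR row, Category 3 is met by any one of K101P, Y181I or Y181V, or alternatively by "Two of: L100I, K101EH, Y181C, G1190E, G190Q, H221Y". Category 2 reads "Includes one of: L100I, K101EH, Y181C, G190E, G190Q, H221Y".

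In the DTG row, the lowest category that uses Q148 is Category 2, which requires "Q148H, Q148K, Q148R + any one of the following" (a list of partner mutations). Categories 3 and 4 require two and three partners. Category 1, headed "Presence of Predictive Mutations but Activity Not Impacted", requires "Two or more of the following: T66A, T66I, T66K E92Q T97A Y143R, Y143C, Y143H V151I N155H".

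The text counts drugs "for which they display mutations corresponding to resistance level (RL) 1-5", whereas Table 2 numbers its categories 1 to 4. The cross-reference that should define RL is broken.

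The score is one of the candidate covariates for the main propensity score (sections 3.3.3 and 4.3). It is one of four named covariates in the matching that replicates the European registry analysis (section 4.5.2).

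**The concern.** Table 2 is an operational scoring rule that a programmer will transcribe, so a wrong mutation code in it can reach the data. The two ETR lists differ in one entry only. If the Category 3 cell is coded as printed, G190E never counts towards high-level resistance, and some people with two listed mutations are scored as having a more active ETR than the table evidently intends. Those people would then be matched, or possibly weighted, on an overstated regimen strength.

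The DTG row and the RL scale raise a related question of completeness. Q148H/K/R without a listed partner falls in no category, and the plan does not say what RL a drug receives in that case.

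**Working it through.** The plan states no score, sample size or power figure that depends on Table 2, so there is nothing to reproduce. The check applies the table's rules literally and then puts the results into Equation 1.

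**Inputs.** The ETR and DTG rows of Table 2, and Equation 1, all from section 3.3.3. Because the step from category to RL is not stated, two mappings are assumed: (a) RL = category, with RL 0 when no category is met; (b) RL = category + 1, with RL 1 when no category is met.

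**ETR: which patterns change.** Take the six Category 2 entries, counting K101E/H as one, and compare the grade as printed with the grade after replacing G1190E by G190E.

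- G190E alone: Category 2 both ways.
- G190E plus exactly one of L100I, K101E/H, Y181C, G190Q or H221Y: Category 2 as printed, Category 3 as corrected. These are five patterns; in one of them (G190E with G190Q) both mutations are at codon 190.
- G190E plus two or more other listed mutations: Category 3 both ways, because the others already satisfy the rule.
- Any pattern with K101P, Y181I or Y181V: Category 3 both ways.

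**ETR: size of the change.** The term is (5 − RL)/5.

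| Mapping | As printed (Category 2) | Corrected (Category 3) | Excess |
|---|---|---|---|
| (a) RL = category | (5 − 2)/5 = 0.6 | (5 − 3)/5 = 0.4 | 0.2 |
| (b) RL = category + 1 | (5 − 3)/5 = 0.4 | (5 − 4)/5 = 0.2 | 0.2 |

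The excess is one RL step, 1/5 = 0.2, under either mapping.

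**DTG: what the table leaves open.** Q148 alone, and Q148 with N155H only, meet no category. A single Category 1 mutation such as N155H also meets none. The DTG term for Q148 alone then depends on a rule that the plan does not give:

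- RL 0 by default: (5 − 0)/5 = 1.0, the same as unmutated virus.
- RL 1 by default: (5 − 1)/5 = 0.8.
- Drug left out of the sum because it has no RL: 0.

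For comparison, two Category 1 mutations give (5 − 1)/5 = 0.8 under (a) and (5 − 2)/5 = 0.6 under (b). Q148 with one partner gives 0.6 under (a) and 0.4 under (b). No corrected DTG value can be computed from the documents.

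**The case against.** The strongest reply on ETR is that G1190E is an obvious slip, that the next cell shows the intended code, and that harm requires someone to program it literally. The replication in section 4.5.2 reuses existing R code, which may already be right, and section 6.2 describes quality checks that may include full code review or independent programming. This limits the likelihood of harm but does not remove the defect. A check of output against specification cannot detect an error in the specification, and the main analysis is not said to reuse that code.

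The reply on impact is sound. In the main propensity score the covariate is only a candidate, alongside separate candidates for the regimen and for resistance. The same table would score both groups, and no mutation frequencies are given.

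A reader might infer more from Table 2, namely that Equation 1 also over-counts DTG because Q148 without a partner is ungraded while two mutations said not to affect activity lower the score. The documents do not support that conclusion. It requires a default RL that is never stated: with RL = category and a default of RL 1, the two patterns both score 0.8, and if ungraded drugs are dropped, Q148 alone scores 0, which would be an under-count if any credit was intended. Dropping ungraded drugs fits poorly with the score's purpose, since unmutated drugs would then also count for nothing, but the text does not exclude it. Leaving Q148 alone ungraded may also be deliberate, because single Category 1 mutations are treated the same way. Assigning it a grade needs resistance evidence from outside the documents.

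**Conclusion.** The ETR error is confirmed on the face of the table. If coded as printed, it overstates the ETR term by exactly 0.2 of a drug for a person on ETR who has G190E, exactly one other listed mutation, and none of K101P, Y181I or Y181V. This assumes that adjacent categories differ by one RL step, as under both mappings tried.

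The score is certain to enter only the section 4.5.2 matching. The number affected is unknown and probably small. A reader might note that five of the 15 possible pairs from the six entries contain G190E and infer that a third of such people are misgraded. That is a count of list combinations, not of people. Neither the size nor the direction of any effect on the risk ratio follows.

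The DTG point stands only as a gap in specification: Q148 without a listed partner has no category, and the plan states neither the mapping from Categories 1–4 to RL 1–5 nor the RL when no category is met. This is a minor correction, worth making because it costs almost nothing.

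**What to change.** 1. In the Category 3 ETR cell of Table 2, change G1190E to G190E. Check that the scoring code, including the R code reused for section 4.5.2, uses G190E, and apply the corrected rule in both the main analysis and the replication.
2. In section 3.3.3, state how Categories 1–4 map to RL and which RL a drug takes when no category is met, and repair the cross-reference.
3. Confirm against the registry algorithm how Q148H/K/R without a listed partner (including Q148 with N155H) is scored for DTG, and write the answer into Table 2. This review does not choose the grade.

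The cost is one corrected table cell, a few lines of text and a check of the matching code, with no new data. If the registry code turns out to carry the G1190E error, the replication can be shown both ways.

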4.1. Bootstrapping

Bootstrapping will be employed to obtain confidence intervals around the study estimates. First, the data will be sampled with replacement to create 500 bootstrap samples. Within each bootstrap sample, multiple imputation will be implemented, producing 10 imputed datasets per bootstrap sample. Within each imputed dataset, analyses will be performed to obtain an estimate at each timepoint for all 5,000 datasets (i.e., 500 bootstrap samples * 10 imputed datasets). The combined estimate will correspond to the average of all 5,000

estimates and the 95% confidence interval will be derived from their distribution, using the 2.5th & 97.5th percentiles.

4.2. Multiple Imputation

OPERA data represent routine clinical care in the US. Therefore, the timing and frequency of follow-up visits and testing varies across patients and providers. Such variations may give rise to a missing data problem in analyses relying on outcomes measured at specific timepoints. While windows have been established around each timepoint of interest to increase the number of VL measurements available for analysis, it remains likely that VL will be missing for different PWH in different time windows.

Complete case analysis in which observations with missing data are omitted is appropriate when data are *missing completely at random* (MCAR; i.e., the missing values do not depend on observed or unobserved data).^[33, 34] With any other type of missing data, despite being the simplest and most commonly used strategy, complete case analysis can lead to severe bias.^[33, 34] In addition, complete case analysis reduces the analytical sample size, thus reducing the efficiency of estimations.^[33]

Limitations of complete case analyses may be alleviated with imputation of missing values when data are *missing at random* (MAR; i.e., the missing values depend on observed data only).^[35] Multiple imputation means that multiple values are imputed for each missing value, resulting in multiple complete datasets. Statistical analyses are then conducted on each imputed dataset, and the results are combined.^[35] Multiple imputation relies on predictive models to predict the missing values based on the observed data. It is therefore important to include all variables that could help predict the missing values.^[18]

Within each bootstrap sample, multiple imputation will be used to ensure that eligible OPERA participants can contribute to all timepoint analyses even if their routine clinical care resulted in VL being measured outside of the ranges defined in the protocol. Missing VLs in OPERA will be handled with multiple imputation implemented using chained equations to produce 10 imputed datasets.

4.3. Propensity score-weighting

PS-weighting uses the PS to up- and down-weight individuals so that the weighted-population resembles the target population.^[36] PS-weighting is advantageous over PS-matching for two reasons. First, the weighting approach allows the utilization of all data available, whereas matching may require the exclusion of individuals who do not have an acceptable match. Matching may thus require a substantially larger sample size, which can be particularly problematic with smaller studies, such as this one.^[37-39] Second, in some circumstances, PS-matching could be more biased: excluding individuals from the analysis may introduce selection bias, and the inability to find an exact match can result in residual

confounding.^[20, 40] Using PS-weighting could thus improve statistical power and reduce the risk of bias in this external comparison study.

An external comparison study such as this one seeks to mimic the results of a hypothetical randomized controlled trial, had such a trial been conducted. Thus, the target population consists in the individuals who were recruited to participate in the trial (i.e., the treated group).^[41] It is therefore important to ensure that the external control group resemble the treated group as closely as possible. The average treatment effect in the treated (ATT) can be estimated using standardized mortality ratio (SMR)-weighting. Of note, both SMR-weighting and PS-matching have been found to closely reproduce estimates from randomized controlled trials.^[20]

SMR-weighting will thus be used to assess the ATT of IBA+OBR compared to non-IBA OBR, ensuring that the distribution of characteristics in the control group is the same as in the treated group.^[20] In other words, the OPERA external control group will be weighted to look like the trial IBA+OBR-treated group. SMR-weighting relies on the PS, which corresponds to the probability for each person to receive IBA+OBR.

Within each imputed dataset, logistic regression will be used to obtain the PS and will include baseline values for important predictors of regimen selection. Continuous variables will be modeled flexibly with either quadratic terms or restricted cubic splines. Candidate covariates for the PS model include age, sex, VL, CD4 cell count, index date, agents in the OBR, resistance to ARVs, and the number of potent ARV in the OBR scaled by level of resistance. SMR weights are set to 1 in the treated population (i.e., IBA+OBR in TMB trials). In the control population (i.e., non-IBA OBR in OPERA), SMR weights are calculated as $PS/(1-PS)$.^[20] The final set of variables included in the PS model will be determined by the distribution of weights, as well as the balance of covariates across groups.

The distribution of weights will be evaluated for the presence of large weights. Model specification will be adjusted to obtain a mean weight as close to 1 as possible and avoid extreme weights. Weight trimming may be considered to reduce the impact of extreme weights.^[42] In such case, trimming would be performed at the 1st and 99th percentile: all weights with a value below the 1st percentile (above the 99th percentile) would be set to the value of the first percentile (99th percentile).^[42] The extent of trimming will be assessed based on the distribution of weights and adjusted as needed. The balance of covariates included in the PS model across groups will be assessed using standardized differences estimated before and after applying the SMR weights. A threshold of <10% will indicate an acceptable balance.^[43]

4.4. Primary Objective: External Comparison of Virologic Effectiveness

The comparative virologic effectiveness of IBA+OBR vs. non-IBA OBR will be assessed at each timepoint for both viral suppression (VL < 200 copies/ml) and undetectability (VL < 50

copies/ml). Within each imputed dataset, estimates of risk will be derived from SMR-weighted Kaplan-Meier curves. The cumulative probability of viral suppression or undetectability will be estimated at each timepoint of interest for each arm, from which risk ratios will be calculated.

The distribution of estimates from all 5,000 datasets will be used to obtain the final estimate (mean) and 95% confidence intervals (2.5th and 97.5th percentiles).

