All TMB-202 and TMB-301/311 trial participants randomized to 800 mg IBA every 2 weeks with or without a loading dose will be included in the main analyses. From the OPERA cohort, adult PWH with resistance from three ARV classes will be considered for inclusion (see section 3.2.1 for more details). OPERA PWH initiating a new non-IBA OBR between 01JAN2008 and 31DEC2020 will be included; person-time will be censored at the first of (a) initiation of a select potent ARV, (b) >45 days without ART, (c) 12 months after last clinical contact, (d) death, or (e) study end (i.e., extract date of the dataset; TBD). Viral suppression (i.e., <200 copies/mL) and undetectable viral load (i.e., <50 copies/ml) will be assessed at each of the timepoints of interest (i.e., weeks 24, 48, 60 and 96), using the closest measurement to the timepoint within a ± 6 -week window.

Statistical Analyses

Multiple imputation will be used to ensure that eligible OPERA participants can contribute to all timepoint analyses even if their routine clinical care resulted in viral loads being measured outside of the ranges defined in the protocol. To prevent the introduction of a bias towards the null, imputation will be performed in the OPERA non-IBA OBR group separately.^[18] 95% confidence intervals will be obtained through bootstrapping.

First, the data will be sampled with replacement to create 500 bootstrap samples. Within each bootstrap sample, multiple imputation will be implemented using chained equations, producing 10 imputed datasets per bootstrap sample.

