Within each imputed dataset, analyses will be performed to obtain an estimate at each timepoint for all 5,000 datasets (i.e., 500 bootstrap samples * 10 imputed datasets). Risk ratios for both viral suppression and undetectability will be estimated as a measure of comparative virologic effectiveness of IBA+OBR vs. non-IBA OBR at each timepoint. The *average treatment effect in the treated* (ATT) will be estimated using standardized mortality ratio (SMR)-weighting, a form of propensity score (PS)-weighting. SMR-weighting ensures that the distribution of baseline characteristics is the same in the control population as in the treated population.^[20] In other words, the external control population will be weighted to look like the treated population. Logistic regression will be used to obtain the PS and will include baseline values for important predictors of regimen selection. SMR weights are set to 1 in the treated population (i.e., TMB trials IBA+OBR) and to PS/(1-PS) in the control population (i.e., OPERA non-IBA OBR).^[20] The final set of variables included in the PS model will be determined by the distribution of weights, as well as the balance of covariates across groups before and after applying SMR weights.

Estimates of risk will be derived from SMR-weighted Kaplan-Meier curves. The cumulative probability of viral suppression or undetectability will be estimated at each timepoint of interest for each arm, from which risk ratios will be calculated. Estimates will be averaged across all datasets to obtain the combined estimate and 95% confidence intervals will be derived from the distribution of all estimates, using the 2.5th & 97.5th percentiles.

These analyses will be repeated for sensitivity objective 1 after restricting the OPERA non-IBA OBR group to PWH with a VL >1,000 copies/mL. For sensitivity objective 2, analyses performed using the European registry data will be replicated as closely as possible, taking into consideration the differences in design between the registry and OPERA datasets.

1. Background and Rationale

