The use of external controls can provide valuable information and context to interpret the results of clinical trials when randomization to a control arm cannot be performed.^[17] However, careful consideration must be given to biases that may be introduced in such analyses. Regional bias, in which patient outcomes differ based on the geographic region due to differences in standard of care or demographic characteristics, can be reduced by selecting external controls in the same region where the trial was conducted.^[17] The Observational Pharmaco-Epidemiology Research & Analysis (OPERA) cohort is a large observational database electronic health record (EHR) from over 143,000 PWH across the US.

It is important to assess the comparative effectiveness of IBA compared to other regimens used in the routine clinical care of HTE PWH with MDR HIV. External comparisons of trial participants and PWH in routine clinical care may help assess the comparative effectiveness of IBA+OBR. Using a comparable external control and larger sample sizes may reduce bias and improve the power of such indirect comparisons. Therefore, an external comparison of IBA+OBR from the TMB-202 and TMB-301/311 trials and non-IBA OBR in routine clinical care in the OPERA cohort may confirm results from prior studies suggesting viral control benefits of IBA+OBR.

2. Study Objectives

Primary Objective

- I. To assess the virologic effectiveness of 800mg IBA every 2 weeks + OBR (TMB-202 & TMB-301/311 trials), compared to other ART regimens in routine clinical care (OPERA cohort), among HTE PWH.
 - External comparison (IBA+OBR in clinical trials vs. non-IBA OBR in OPERA)
 - Timepoint analysis
 - Multiple imputation of missing viral loads in OPERA
 - PS standardized mortality ratio-weighting

Sensitivity Objectives

- I. To assess the robustness of results from the primary objective to the viremia threshold for inclusion in the OPERA non-IBA OBR group (main: VL >1,000 copies/mL vs. sensitivity: VL >200 copies/mL).
- II. To replicate previous analyses of the European registry as closely as possible, taking into consideration the differences in design between the registry and OPERA datasets
 - External comparison (IBA+OBR in clinical trials vs. non-IBA OBR in OPERA)
 - Timepoint analysis
 - Complete case analysis
 - Propensity score matching (PS including baseline VL, CD4 cell count, number of potent ARVs scaled by the level of resistance, and the calendar period score)

3. Study Design

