4.5. Sensitivity Analyses

4.5.1. Impact of the viremia threshold in the OPERA non-IBA OBR group

In the TMB-202 and TMB-301/311 trials, the protocol restricted trial participation to individuals with a VL >1,000 copies/mL at baseline. However, in practice, individuals with a baseline VL ≤1,000 copies/mL were recruited. In routine clinical care, changes in regimen often occur before a threshold of VL >1,000 is reached. Therefore, to maximize the sample size and align with the population recruited in the trials, the main analysis will include PWH with a viral load > 200 copies/mL at the start of the index regimen in the OPERA non-IBA OBR group. However, to assess the impact of this more lenient threshold, a sensitivity analysis will be conducted in which the OPERA non-IBA OBR group will be restricted to PWH with a VL >1,000 copies/mL at index, as was intended for the trials.

Analyses described in sections 4.1-4.4 will be repeated after restricting the OPERA non-IBA OBR group to those with an index VL >1,000 copies/mL. New bootstrap samples and imputed datasets will be generated, within which SMR-weighted risk ratios will be estimated before being combined in a final estimate.

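### The outcome is viral load status at weeks 24, 48, 60 and 96, but Section 4.4 estimates a cumulative Kaplan-Meier probability with no event, event time or trial-arm censoring rule

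*Combined protocol and SAP*

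**What the plan says.** **Outcome.** Section 3.3.2 lists two thresholds, <200 and <50 copies/mL, and gives the timing as "Weeks 24, 48, 60, 96 after index (closest measurement within a" window of six weeks either side). The Study Design part of the opening summary agrees: status is assessed "using the closest measurement to the timepoint within a" window of that width. Section 2 labels the primary analysis "Timepoint analysis". Section 4.2 states the purpose of imputation in the same terms: "multiple imputation will be used to ensure that eligible OPERA participants can contribute to all timepoint analyses".

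**Estimator.** Section 4.4 says that within each imputed dataset "estimates of risk will be derived from SMR-weighted Kaplan-Meier curves", and the Statistical Analyses part of the summary says the same. Section 4.4 adds: "The cumulative probability of viral suppression or undetectability will be estimated at each timepoint of interest for each arm". Risk ratios are formed from these probabilities.

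**Censoring and follow-up.** Section 3.2.2 lists censoring criteria for OPERA, death among them, and none for the trials. It ends TMB-202 follow-up at week 24 and TMB-301/311 follow-up at week 96. Section 3.1.2 reports that 27 US patients of the 40 in TMB-301 entered TMB-311, with four deaths during TMB-301 and two during TMB-311.

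**Sensitivity analyses.** Section 4.5.1 states: "Analyses described in sections 4.1-4.4 will be repeated after restricting the OPERA non-IBA OBR group". Section 4.5.2 is a matched complete-case analysis that uses existing R code from the European registry study.

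**The concern.** A status outcome can go down as well as up: someone suppressed at week 24 may be viremic at week 96. A cumulative probability from a Kaplan-Meier curve can only rise. Such a curve needs an event, an event time and a censoring rule in each arm. The plan supplies the thresholds and the OPERA censoring rules only. Rebound is mentioned in the background (Section 1) but not in the outcome or the analysis.

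On the first-event reading, viral loads after first suppression play no part, whether observed or imputed. That works against the stated purpose of the imputation. In the treated arm, people in TMB-202 who are suppressed at week 24 are carried forward as successes to weeks 48, 60 and 96, although no viral load is planned for them then.

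Readers will take the week 48, 60 and 96 risk ratios as the relative probability of being suppressed at that week. If rebound differs between arms, they are not. Two programmers could also code Section 4.4 differently and both claim to have followed it.

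**Working it through.** **The plan's own figures.** Section 5: 59 + 40 = 99 treated. Section 4.1: 500 × 10 = 5,000 datasets. Both reproduce. There is no power calculation to check.

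**Treated follow-up after week 24.** TMB-202 contributes 59/99 = 60% of the treated group and has no planned follow-up after week 24. At most 27/99 = 27% have follow-up beyond it. TMB-301 enrolled 34 in the US, 4 in Taiwan and 2 in Puerto Rico. The 27 entrants are described as US patients, so the other 4 + 2 = 6 may have had no route into the extension.

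**Illustration.** All rates are assumptions: 50% (IBA) vs 40% (control) suppressed at week 24, and 15% of those not suppressed becoming suppressed in each later interval (24–48, 48–60, 60–96). Rebound varies, and nobody is censored.

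- Ever suppressed (first-event Kaplan-Meier): E′ = E + (1 − E) × 0.15
- Suppressed at the timepoint (status): P′ = P × (1 − rebound) + (1 − P) × 0.15

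Ever suppressed at weeks 48/60/96 is 0.575/0.639/0.693 for IBA and 0.490/0.566/0.632 for control. The risk ratios are 1.17/1.13/1.10. Rebound does not enter the formula.

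| Rebound per interval, IBA vs control | Status RR, week 48 | week 60 | week 96 |
|---|---|---|---|
| 10% vs 10% | 1.17 | 1.12 | 1.08 |
| 30% vs 30% | 1.15 | 1.09 | 1.05 |
| 10% vs 15% | 1.22 | 1.21 | 1.20 |
| 15% vs 10% | 1.11 | 1.03 | 0.97 |

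The week-96 entries for the first, third and fourth rows are 0.558/0.516, 0.558/0.466 and 0.500/0.516.

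**Break-even.** With control rebound of 10%, the status risk ratio falls below 1 only if IBA rebound exceeds 25% (week 48), 16.5% (week 60) or 13.6% (week 96). The week-96 value is 15.3% or 12.3% if new suppression is 5% or 25% per interval.

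**Levels.** With 20% rebound in both arms, week-96 Kaplan-Meier shows 69% vs 63%, while 45% vs 42% are suppressed.

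**Values not used.** If events are read at the timepoints, the share of control viral loads that no longer matters is the share already suppressed once: 40% at week 48 and 57% at week 96.

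**Other assumed rates.** With new suppression of 15%, 10% and 10% in the three intervals and no re-suppression after rebound, the week-96 Kaplan-Meier ratio is 1.12. The status ratio runs from 0.73 (rebound 20% IBA vs 5% control) to 1.65 (5% vs 20%).

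**Precision at week 96**, with 10% rebound in both arms and effective control size m (an assumption):

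- Status: SE of log RR = √[(1 − 0.558)/(27 × 0.558) + (1 − 0.516)/(m × 0.516)]. At m = 100 this is 0.197, giving 0.74–1.59.
- Kaplan-Meier: Greenwood for the treated arm, with 99 at risk at week 24 and then 13.5, 11.5 and 9.8 (half of the 27 entrants, falling by 15% each time). For controls, (1 − 0.632)/(m × 0.632). At m = 100 the SE is 0.130, giving 0.85–1.42.
- At m = 50: 0.70–1.66 against 0.82–1.48. At m = 200: 0.75–1.55 against 0.87–1.38.

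Variability of the weights would widen all of these.

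**The case against.** **Time to first suppression is a legitimate outcome, and Kaplan-Meier keeps TMB-202 in the analysis.** This stands. The documents require that outcome and estimator agree, not that one of them wins. The late precision of Kaplan-Meier, however, comes largely from carrying week-24 successes forward rather than from late data on the outcome in Section 3.3.2.

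**The curve could be coded as status in each window.** It could, but then the text has to say so, and the result would no longer be a cumulative probability.

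**With equal rebound the risk ratios hardly differ.** True: 1.10 against 1.08 at 10% rebound, and 1.10 against 1.05 at 30%. The arm-level probabilities are still overstated.

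Four stronger readings are tempting but not supported:

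- A reader might infer that the plan favours IBA or hides a reversal. The documents give no rates from which to say so. The 0.97 above is close to null, needs higher rebound on IBA, and lies well inside the status interval calculated for equal 10% rebound (0.74–1.59).
- A reader might infer that all four timepoints are compromised. If only timepoint values enter the curve, week 24 agrees under both readings. It would differ only if an earlier viral load could count as the event.
- A reader might infer from the 13 of 40 TMB-301 participants who did not enter TMB-311 that counting losses as failures would by itself push the risk ratio below 1. That requires penalising the treated arm alone. The same proportion lost in both arms multiplies both probabilities equally and leaves the ratio unchanged.
- A reader might infer that no planned analysis compares status. For sensitivity objective 2 this cannot be determined. Section 2 calls it a timepoint analysis, but its estimator lies in code outside the documents. Sensitivity objective 1 repeats Sections 4.1–4.4 and so inherits the conflict.

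**Conclusion.** The point holds and should be settled before any estimate is produced. The stated primary estimator does not match the stated outcome, and three of the four timepoints (weeks 48, 60 and 96) are exposed on the ordinary first-event reading. The text conflict rests on no assumption. Its numerical effect does: size and direction are unknown, and the figures above show only that the two quantities nearly agree when rebound is equal and separate when it is not. Under the main set of assumed rates, the week-96 Kaplan-Meier ratio of 1.10 corresponds to status ratios from 0.97 to 1.20.

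The thin late follow-up in the treated arm is a related but separate gap. It makes the choice of estimator matter more and will limit any week 48–96 estimate, whichever option is taken.

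**What to change.** Make Sections 3.3.2 and 4.4, and the matching summary text, agree in one of two ways.

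**Preferred: estimate status.**

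1. Replace the Kaplan-Meier step with the SMR-weighted proportion below 200 (and 50) copies/mL at each timepoint, in the same 5,000 datasets.
2. State one rule for death and one for other loss, applied to both arms, and a rule for missing trial viral loads.
3. Report the number observed, dead and lost, by arm and timepoint.
4. State that all treated data after week 24 come from TMB-311 entrants. Then choose how to present weeks 48–96. One choice is to keep all 99 as the target and state the extrapolation to TMB-202 and to the 6 non-US TMB-301 participants. Censoring weights cannot be estimated within TMB-202 and may not be estimable for those six. The other is to present estimates for a restricted population, with controls re-weighted to it.

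The cost is a rewrite of Section 4.4, some added modelling for loss, and wider late intervals: about 0.74–1.59 instead of 0.85–1.42 at week 96, with an assumed effective control size of 100.

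**Equally acceptable: keep Kaplan-Meier.** Define the event, its time, trial-arm censoring and how death counts. Rename the outcome time to first suppression (and to first undetectability), show numbers at risk, and make no claim about status at a given week. The cost is text and an at-risk table, and the status-at-week outcome is given up.

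Under either option, state in Section 4.5.2 which estimator the replication uses.
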